Aim 4c. To assess the effectiveness of the MBST intervention compared to a psychoeducational intervention (active control) at reducing the perpetration of dating violence. We hypothesized that the MBST intervention will be more effective at reducing dating violence perpetration (physical, sexual, and psychological) as compared to the psychoeducational intervention.

Methods

Participants

100 participants were recruited through Kent State University's online subject pool. Sample size was determined using G*Power3 (Faul, Erdfelder, Lang, & Buchner, 2007). Ninety-one participants completed the initial baseline assessment, and three participants were excluded from the rest of the study for not meeting inclusion criteria (see below; 2 indicated being single, 1 indicated being married). Thus, this study reports on the remaining 88 participants' data.

To be eligible, participants were required to be over the age of 18, in a current dating relationship (of 6 months or longer) and were required to confirm that they had *not* been

diagnosed with psychopathology (Major Depressive Disorder, Post-Traumatic Stress Disorder, Borderline Personality Disorder). At baseline, participants did not differ between assigned treatment groups based on age, ethnicity, gender, depression, anxiety, externalizing behavior problems, or substance use.

Furthermore, only one member of the dating couple could participate in the study. To address issues surrounding contamination, participants were reminded throughout the course of the study that they could not discuss the intervention with anyone (except their romantic partner) until the end of the study.

Data collection was conducted online (except for the first two homework assignments which were handed in using paper copies, used for compliance data; see Data and Safety Monitoring Plan for details surrounding homework collection). Participants were asked to complete online surveys in private, though they could choose where that was (e.g., dorm room or elsewhere). The actual intervention took place on Kent State University's campus, specifically classrooms in Kent Hall (rooms 60, 102, 145, and 167). This study was approved by Kent State University's Institutional Review Board.

Trial design

This study utilized a two-armed, parallel-design. The allocation ratio was 1:1. The treatment group was the MBST intervention and the active control group was the psychoeducational intervention.

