Social desirability. To assess social desirability (which may impact participants’ self-reporting biases), the Marlowe-Crowne Social Desirability Scale was used (Crowne & Marlowe, 1960). Participants were asked to quickly respond to 33 True/False items such as “Before voting I thoroughly investigate the qualifications of all the candidates” and “If I could get into a movie without paying and be sure I was not seen, I would probably do it” (reverse scored). Every time a participant indicated “true”, his/her score increased by one point. All items were summed, with higher scores indicating a greater concern with social approval. This scale demonstrates good internal consistency and ($\alpha = 0.88$) test-retest reliability over a one-month period ($\alpha = 0.89$) (Crowne & Marlowe, 1960).

Intervention Sessions: Homework/Compliance.

MBST intervention. To assess compliance with the intervention, we collected data on whether participants in the MBST condition completed and handed in their homework. For the MBST intervention, 24 participants attended every single session and completed every single homework assignment.

Psychoeducational intervention. To assess compliance with the intervention, we collected data on whether participants in the psychoeducational condition completed and handed in their homework. For the psychoeducational intervention, 26 participants attended every single session and completed every single homework assignment.

Daily Diary: Application of Knowledge and Skills.

MBST intervention group's use of ABCDE skills. To assess if participants were using the skills taught in the intervention, participants were asked every day for seven days about whether they used the A, B, C, D, and/or E skill.

Psychoeducational intervention group's identification of dating abuse. To counterbalance the time spent completing daily diaries, the psychoeducational intervention group also completed a seven-day daily diary that asked whether they had seen examples of dating abuse in the media and to describe who was the bystander, target, and abuser in each example. See appendix for full survey.

Follow-up: Outcome variables.

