Dating violence. The Conflict in Adolescent Dating Relationships Inventory (CADRI, Wolfe et al., 2001) was used to assess dating violence perpetration. This measure assesses dating violence that has occurred over the past month. There are five subscales that assess physical abuse, sexual abuse, verbal or emotional abuse (to assess psychological dating violence), threatening behavior, and relational aggression. There are also 10 items that assess conflict resolution behaviors to add balance. The CADRI has demonstrated adequate reliability, validity, and inter-partner agreement (Wolfe et al., 2001) and has been used in college samples in previous works (e.g., Roudsari, Leahy, & Walters, 2009; van Dulmen, Mata, & Klipfel, 2012). This measure was also used at baseline (to control for initial levels of dating violence).

Mindfulness skills. To assess mindfulness skills, participants completed the Kentucky Inventory of Mindfulness Skills (KIMS; Baer, Smith, & Allen, 2004). This measure has a total of 39 items with four subscales that map onto our conceptualization of mindfulness: observing (e.g., I notice when my moods begin to change), describing (e.g., I'm good at finding the words to describe my feelings), accepting without judgment [e.g., I criticize myself for having irrational or

inappropriate emotions (reverse scored)], and acting with awareness (e.g., When I'm doing something, I'm only focused on what I'm doing, nothing else). Participants rated each statement on a 5-point Likert scale (1 = never or very rarely true, 5 = almost always or always true). Items that describe the absence of the component of mindfulness were reverse scored. This scale has demonstrated good internal consistency, test-retest reliability, and validity (Baer et al., 2004). Mindfulness skills were also assessed at baseline (to control for initial levels of mindfulness skills). These scales demonstrated fair to good internal consistency for observing at baseline ($\alpha = 0.80$) and follow-up ($\alpha = 0.90$), describing at baseline ($\alpha = 0.88$) and follow-up ($\alpha = 0.84$), accepting without judgment at baseline ($\alpha = 0.86$) and follow-up ($\alpha = 0.93$), and acting with awareness at baseline ($\alpha = 0.76$) and follow-up ($\alpha = 0.73$).

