Aim 3. To assess whether participants in the MBST intervention improved their emotion regulation (a manipulation check), we examined mean differences using paired t-tests with covariates. These tests compared the means of emotion regulation subscales at baseline to the mean of emotion regulation subscales at follow-up, controlling for covariates identified in preliminary analyses. Please note this analysis only included participants who were assigned to the MBST intervention (and did not include those in the psychoeducational intervention). Tests were run individually for all six subscales (lack of emotional awareness [DER – EA], lack of emotional clarity [DER – EC], nonacceptance of emotional responses [DER – NE], impulse control difficulties [DER – IC], limited access to emotion regulation strategies [DER – ER], and difficulties engaging in goal-directed behavior [DER – DE]). Please note that a *decrease* in means indicates improvement, as higher scores on the Difficulties in Emotion Regulation Scale indicate more problems with emotion regulation.

Aim 4a. To assess whether participants in the psychoeducational intervention reduced dating violence perpetration from baseline (before the intervention) to follow-up (after the intervention) we examined paired t-tests with covariates. These tests compared the mean of dating violence perpetration at baseline to the mean of dating violence perpetration at follow-up, controlling for covariates identified in preliminary analyses. Please note this analysis only included participants who were assigned to the psychoeducational intervention (and did not include those in the MBST intervention). Please also note analyses were run separately for each type of dating violence (physical, sexual, psychological).

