Aim 4b. To assess whether participants in the MBST intervention reduced psychological dating violence perpetration from baseline (before the intervention) to follow-up (after the intervention) we examined mean differences using paired t-tests with covariates. These tests compared the mean of dating violence perpetration at baseline to the mean of dating violence perpetration at follow-up, controlling for covariates identified in preliminary analyses. Please note this analysis only included participants who were assigned to the MBST intervention (and did not include those in the psychoeducational intervention). Please also note analyses were run separately for each type of dating violence (physical, sexual, psychological).

Aim 4c. We used a regression framework to investigate the effectiveness of the MBST intervention at reducing dating violence perpetration as compared to the psychoeducational intervention. We chose to run my analyses within a regression framework in Mplus as this allowed for intercorrelations among predictors (e.g., anxiety and depression were included as covariates so we could account for their intercorrelation) and the use of FIML to handle missing data. We used dummy coding to create a variable to differentiate treatment groups. Within a regression framework, we used this dummy-coded variable to predict our outcome (dating violence). We controlled for baseline levels of dating violence perpetration and included other covariates based on preliminary analyses. This analysis, as compared to the analyses for Aims 1 – 3, included participants from both groups. Please also note analyses were run separately for each type of dating violence (physical, sexual, psychological).

Intent to treat analyses. As guided by the Consolidated Standards of Reporting Trials (CONSORT; Schulz, Altman, & Moher, 2010), the number of participants in each group were analyzed according to the intent-to-treat (ITT) principle. ITT is a collective strategy for design, conduct, and analysis in which all participants who are randomized to a group are treated as if

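### Physical and sexual perpetration in Aims 4a to 4c are tested with paired t-tests and what reads as linear regression, with no safeguard if few participants score above zero

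*Combined protocol and SAP*

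**What the plan says.** - **Outcome.** Measures (Dating violence) uses the CADRI at baseline and follow-up: "This measure assesses dating violence that has occurred over the past month". No prevalence, mean, standard deviation or scoring rule is given.
- **Aims 4a and 4b.** Within each arm, baseline and follow-up means are compared by paired t-tests with covariates.
- **Aim 4c.** "Within a regression framework, we used this dummy-coded variable to predict our outcome (dating violence", controlling for baseline perpetration and screened covariates, in Mplus with FIML. No link, distribution or estimator is stated.
- **All three.** "analyses were run separately for each type of dating violence (physical, sexual, psychological".
- **Prediction.** Aims and Hypotheses expects the psychoeducational reduction (Aim 4a) not to reach significance and the MBST reduction (Aim 4b) to do so.
- **Size.** "100 participants were recruited through Kent State University's online subject pool"; "Thus, this study reports on the remaining 88 participants' data". "The allocation ratio was 1:1".

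The Analysis Plan names no transformation, distribution check, count, binary or two-part model, permutation test or robust estimator. FIML deals with missing values, not with zeros.

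**The concern.** Recall covers one month. The sample is a general student pool, not selected for violence, and people with three listed diagnoses are excluded. Physical and sexual scores, taken singly, could well be zero for most participants. A test of means then depends on a handful of people, and the normal approximation behind its p-value may fail.

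The stake is greatest where non-significance is itself the prediction. If a test cannot reject, Aim 4a's hypothesis appears confirmed whatever the programme did. The contrast the trial hopes to see, significant in one arm and not in the other, could also turn on one participant.

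**Working it through.** **Inputs.** The 88 participants at 1:1 give about 44 per arm (arm sizes are not stated). Follow-up numbers are not stated either, so 25 per arm serves as an assumed low case: for MBST "24 participants attended every single session and completed every single homework assignment", and 26 did so in the psychoeducational arm. Two-sided 0.05 is assumed, since the plan states .05 only for covariate screening. The share above zero is assumed, from 2% to 50%.

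**The plan's own figure.** "Sample size was determined using G*Power3", but no effect size, power, alpha or test is given. The 100 cannot be reproduced and says nothing about sparse scores.

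**Within an arm (Aims 4a, 4b), plain paired t.** Let k of n=44 change, all in one direction and by the same amount. Then t = √[(n−1)k/(n−k)] on 43 df, and the exact sign-flip p is 2×(1/2)^k.

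| k | t | t-test p | exact p |
|---|---|---|---|
| 3 | √(43×3/41)=1.77 | 0.083 | 0.25 |
| 4 | √(43×4/40)=2.07 | 0.044 | 0.125 |
| 5 | √(43×5/39)=2.35 | 0.024 | 0.063 |
| 6 | √(43×6/38)=2.61 | 0.013 | 0.031 |

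Three or fewer cannot reach .05. With 25 in the arm, k=3 again gives 0.083.

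**Between arms, no adjustment, equal scores, 44 v 44.** For a 4 v 0 split the mean difference is 4/44=0.0909 and its standard error is √[(4−16/44)/86 × 2/44]=0.0438. So t=2.07 and p=0.041. The exact p is 2×C(44,4)/C(88,4) = 271,502/2,331,890 = 0.116. For 5 v 0, t-test p=0.021 and exact p=0.055.

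Adding the hypergeometric probabilities of every split that the t-test rejects gives its actual error for a given total k: 0% (k=2 or 3), 11.6% (4), 5.5% (5), 2.6% (6), 11.0% (7), 8.9% (10).

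**Relaxing those two conditions.** Simulated error for the same totals:

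| Condition | k=4 | k=7 | k=10 |
|---|---|---|---|
| Scores 1 or 2 at random, unadjusted | 4.3% | 6.1% | 4.7% |
| Skewed scores, unadjusted | 1.1% | 3.7% | 4.1% |
| Equal scores, baseline-adjusted | 3.2% | 6.0% | 4.1% |
| Skewed scores, baseline-adjusted | 2.2% | 3.3% | 3.8% |

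The adjusted rows assume that about half of those positive at follow-up were also positive at baseline.

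**Averaged over k.** Simulation with 20,000 null trials per cell; positive scores are rounded-up exponentials (scale 2), and the latent baseline to follow-up correlation is 0.5.

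| Share above zero | Adjusted regression, 44/arm | Same, 25/arm | Paired t, n=44 | Paired t, n=25 |
|---|---|---|---|---|
| 2% | 0.3% | 0.04% | 0.1% | 0.01% |
| 5% | 1.9% | 0.6% | 1.1% | 0.3% |
| 10% | 3.6% | 2.3% | 3.2% | 1.5% |
| 20% | 4.4% | 3.9% | 4.1% | 3.3% |
| 50% | 4.9% | 4.6% | 4.7% | 4.7% |

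The regression columns use the ordinary t reference. The maximum-likelihood z that Mplus would give by default is slightly higher (2.5% at 5% and 4.4% at 10%, 44 per arm), and a robust sandwich z is nearly the same (2.4% and 4.5%).

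**The case against.** A reader might infer from the 11 to 12% figures that chance produces significance far more often than 5% in this trial. The documents do not support that. Those figures need identical scores and no adjustment, whereas Aim 4c adjusts for baseline and analyses mean scores. Relaxing either condition brings the error to about 6% or less at the totals tabulated, and averaged over counts the test is conservative to nominal.

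Two further readings also go too far. First, the text does not call the Aim 4c regression linear; that is the natural reading, but the firm point is that the model is unspecified. Second, the documents do not show that most scores are zero. Conditioning on the number of perpetrators does not remove that assumption, and the Objectives call dating violence on campuses prevalent.

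It is also fair to say that exact tests do not restore missing information. With equal scores and no adjustment, the exact between-arm test cannot reject below six positives (p=0.055 at 5 v 0), and the sign-flip test cannot reject below six changers. The t-tests can reject from four. A robust standard error is not shown to help.

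What stands is that the paired t-tests are explicit, nothing in the plan covers sparse scores, and the reading of non-significance under Aim 4a is unprotected.

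**Conclusion.** This is a worthwhile, cheap improvement and not a demonstrated error. If few participants score above zero, the planned p-values for physical and sexual violence are unreliable, mostly by rejecting too seldom: about 2% actual error at 5% prevalence with skewed scores and 44 per arm. They are near nominal once roughly 10 to 20% score above zero. Psychological violence is unaffected if most participants score above zero, which is also not stated.

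The sharpest consequence is within arms. Three equal-scoring perpetrators all stopping gives p=0.083, and four gives p=0.044. One person can therefore produce the predicted contrast between Aims 4a and 4b, while the exact p-values are 0.25 and 0.125. These figures assume about 44 per arm, no new perpetrators and no covariates. The simulated ones also depend on the assumed severity distribution and correlation.

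**What to change.** 1. State the distribution and estimator for Aim 4c. Keep the baseline-adjusted arm coefficient, but take its p-value from re-randomising arm within semester, which mirrors the allocation under Randomization.
2. For Aims 4a and 4b, replace the normal-theory p-value with a sign-flip (exact paired permutation) test. Re-randomising arm cannot supply a p-value for a single-arm comparison.
3. Report the number scoring above zero by arm and time point, with an exact any/none comparison for physical and sexual violence.
4. State that a non-significant result with few perpetrators is inconclusive and does not support the Aim 4a hypothesis.

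**Cost.** A short script and some wording; no new data. Under the null that arm has no effect, the re-randomisation p-value holds its level at any prevalence. In one simulation with skewed scores, 10% above zero and 44 per arm, it raised power from 14.6% to 21.6%; the gain depends on the assumed effect. Power falls slightly if non-zero scores are nearly equal, and any/none discards severity. The sign-flip test uses only participants with both scores, so show it beside the FIML estimate of change. The document is written in the past tense: if the planned tests have been run, report both sets and label the new ones as added.

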Participants were recruited to complete a baseline assessment, an intervention portion (consisting of three 50-minute sessions with homework in-between sessions), a seven-day daily diary, and a follow-up assessment. All participants completed the initial baseline assessment the fourth week of classes. During this assessment, data was collected on demographics, dating

violence (during the past month), emotion regulation, mindfulness skills, attitudes condoning dating violence, and other potential covariates (relationship length, relationship satisfaction, externalizing behavior problems, anxiety, depression, substance use, use of mindfulness practices in the past month, social desirability).

Following this baseline assessment, participants were randomized into either (1) the MBST intervention or (2) the psychoeducational intervention. Each intervention consisted of three 50-minute sessions that occurred during the sixth, seventh, and eighth week of the semester. In-between sessions all participants were asked to complete homework. Homework assignments were turned in the following week, with the final homework assignment being completed online as part of the first daily diary (since participants did not meet physically the week following the final session). There were two semesters of data collection total. All intervention sessions occurred at the same time (6:00 – 6:50 PM) on Tuesday nights. Conditions were counter balanced with graduate students leading the sessions, social support of groups, and homework. We attempted to counter balance based on room location, but the availability of rooms changed between semesters. However, no treatment condition was given in the same room twice and rooms were selected to be as similar as possible (number of desks, void of windows, etc.).

The week following the final intervention session, participants completed a seven-day daily diary assessment. During this assessment, participants in the MBST intervention were asked to report whether they had used any of the skills learned in the intervention (see below for detailed information on skills), and to describe what happened when they used the skill(s) (who they were with, if it helped, etc.). To balance the conditions, participants in the psychoeducation intervention were asked to indicate whether they had seen any examples of dating abuse in the

media that day. If they had, they were asked to describe who the victim, target, and bystanders were in each example.

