Session 2. At the beginning of the session, students briefly discussed their reactions to last week's homework. After reviewing the A and B skills, they were introduced to the C skill: checking in with their feelings and thoughts. This skill taught them how to accept their own internal experience without judgment and to describe their experience by putting it into words. They were informed that checking in with their feelings and thoughts would help them gain clarity and insight into the emotions they feel, as well as any thoughts surrounding those emotions. They were instructed to curiously ask themselves "What am I feeling?" and to answer it as if they were observing themselves from a distance. They were informed that this practice (which captures decentering) would help them to see the situation more objectively and would give their feelings less power over them. Indeed, observing and labeling feelings in this way decreases the intensity and duration of the emotions. They were given examples of how to check in with their feelings and then were given time to practice. Then they extended the practice to thoughts that they might be having using the same mindset (nonjudgmentally observing, as if from a distance). They were asked to observe their thoughts by making statements such as "I had the thought that my partner didn't care about me" instead of "My partner didn't care about me." They were given examples of how to check in with their thoughts, and then were given time to practice. Students then briefly reviewed the ABC skills and were given their homework (to

continue practicing awareness and breathing, but to also check in with their feelings and thoughts at least three times that week and to complete a worksheet about it).

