Psychoeducational intervention. The Love is Not Abuse (LINA) curriculum (Liz Claiborne Education Development Center (n.d.)) was used as the psychoeducational treatment. The curriculum was created in conjunction with a variety of organizations (e.g., Break the Cycle, the National Network to End Domestic Violence). The curriculum can be modified depending on the time frame available; each section can be used on its own, or different pieces of information from each section can be put together to be conducted in just one session. The selected materials covered (a) what dating abuse¹ is (b) the pattern of abuse and (c) technology and dating abuse. The curriculum is interactive and includes handouts, activities, and discussion. Materials were selected based on what could feasibly be implemented within three 50-minute sessions. Portions that were excluded are as follows: a portion that informs students how they can intervene to help a friend or family member who is being abused, a portion that informs students how they can intervene to help a friend or family member who is abusing, discussing obstacles that young adults face in seeking help (e.g., not wanting to lose social status that might come with the relationship), reading a poem about the cycle of dating abuse to identify phases in the cycle, and discussing password-sharing and sexting as ways students use to show intimacy and trust in a relationship. An advanced PhD student lead the sessions, but the curriculum was designed so that anyone (teacher, staff member, etc.) would be able to deliver it. Below is a description of what was included in the intervention (see appendices for full intervention materials)

Session 1. During the first session (What is Dating Abuse?), students were introduced to the program and were given ground rules for the session (e.g., no question is stupid or wrong; no

¹ Here, we use the term “abuse” as that is the terminology used in the LINA program. While “dating violence” is used throughout the paper, we maintain the word “abuse” in order to maintain the program’s fidelity.

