Emotion regulation. We assessed emotion regulation using the Difficulties in Emotion Regulation Scale (DERS; Gratz & Roemer, 2004). This scale asked participants to indicate how often a series of items applies to them (36 items total), rated on a 5-point scale (1 = almost never, 2 = sometimes, 3 = about half of the time, 4 = most of the time, 5 = almost always). The six subscales are: lack of emotional awareness [e.g., “When I’m upset, I take time to figure out what I’m really feeling” (reverse scored)], lack of emotional clarity (e.g., “I have difficulty making sense out of my feelings”), nonacceptance of emotional responses (e.g., “When I’m upset, I become angry with myself for feeling that way”), impulse control difficulties (e.g., “When I’m upset, I lose control over my behaviors”), limited access to emotion regulation strategies (e.g., “When I’m upset, believe that wallowing in it is all I can do”), and difficulties engaging in goal-directed behavior (e.g., “When I’m upset, I have difficulty thinking about anything else”). Higher scores indicate more difficulties with emotion regulation. Emotion regulation was also assessed at baseline (to control for initial levels of emotion regulation).

Potential contamination. At the end of the study, all participants were asked whether they spoke to other students about their treatment condition (yes/no). Four participants indicated they discussed their treatment condition with other students.

Potential threat to non-independence of data. Participants were also asked to indicate whether their romantic partner participated in the same research study (yes/no). No participants indicated that their partner also participated in the study.

Participants' belief about treatment assignment. At the end of the study, all participants were asked whether they believed they were in the treatment group or the control group.

Analysis Plan

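### Aim 4c treats students taught together in shared classes as independent, so its standard error is too small if outcomes correlate within class for reasons other than the leader; a smaller point is that semester, within which allocation was balanced, is left out.

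*Combined protocol and SAP*

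**What the plan says.** **Delivery.** The Participants section places the sessions on campus, "specifically classrooms in Kent Hall (rooms 60, 102, 145, and 167" being the rooms listed. Under Trial design, "All intervention sessions occurred at the same time" (one Tuesday evening slot), and "There were two semesters of data collection total". The same section says that session leaders were counterbalanced across conditions, that room counterbalancing was attempted but room availability changed between semesters, and that neither condition used any room more than once.

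**Interaction in class.** In MBST Sessions 2 and 3, "At the beginning of the session, students briefly discussed their reactions" to the previous homework. Of the psychoeducational arm the plan says: "The curriculum is interactive and includes handouts, activities, and discussion".

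**Allocation.** The Randomization section describes individual allocation of each semester's list into two equal halves, one per condition, repeated each semester.

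**Analysis.** Aim 4c is a single-level regression in Mplus, run separately for physical, sexual and psychological violence. Besides the treatment dummy: "We controlled for baseline levels of dating violence perpetration and included other covariates based on preliminary analyses". The screened covariates under Preliminary analyses include neither semester nor class.

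**Non-independence.** The one check under that name concerns couples: "Participants were also asked to indicate whether their romantic partner participated in the same research study".

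**The concern.** Individual randomisation makes participants exchangeable before the sessions. It does not keep them independent afterwards, once about half of each semester's students have shared a room, a leader and a discussion for three sessions. If those shared experiences move classmates' follow-up scores together, the treatment contrast varies more than a participant-level regression allows for, and the test rejects too often. Aim 4c is the only randomised comparison of the two interventions, so this is where a false positive would matter most.

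Semester is a separate and smaller matter. Allocation was balanced within semester, so the matching analysis would include it. Leaving it out puts any semester difference into the residual and makes the standard error too large. The two effects act in opposite directions.

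**Working it through.** **No plan figure to reproduce.** The plan gives no ICC, design effect, number of classes or significance level for Aim 4c. The recruited 100 is attributed to G*Power3 with no inputs, so it cannot be reproduced. A two-sided 5% test is assumed throughout; the only .05 threshold in the text is for covariate screening.

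**Number of classes (inferred).**
- Minimum: 2 conditions × 2 semesters = 4.
- Loose ceiling: 4 rooms × 1 weekly slot × 2 semesters = 8.
- Eight fits poorly. It needs all four rooms in both semesters, and with no condition using a room twice the conditions would have to exchange rooms completely. That is full room counterbalancing, which Trial design indicates was not achieved. One half-list per condition per semester, with four named rooms, points to four.

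**Class size m, assumed equal.** All 88 participants in four classes: 88/4 = 22. Only those who attended every session and completed all homework (24 + 26 = 50), as an illustration of attrition: 50/4 = 12.5.

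**Inflation with no leader component.** Design effect DEFF = 1 + (m − 1) × ICC; type I error = 2 × [1 − Φ(1.96/√DEFF)].

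| Assumed ICC | m = 22: DEFF | SE should be × | Type I | m = 12.5: DEFF | Type I |
|---|---|---|---|---|---|
| 0 | 1.00 | 1.00 | 5.0% | 1.00 | 5.0% |
| 0.01 | 1.21 | 1.10 | 7.5% | 1.115 | 6.3% |
| 0.02 | 1.42 | 1.19 | 10.0% | 1.23 | 7.7% |
| 0.05 | 2.05 | 1.43 | 17.1% | 1.575 | 11.8% |

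A 20,000-run simulation of the planned model (normal outcomes, baseline correlation 0.5, four classes of 22) gave 4.9%, 7.5%, 10.3% and 17.4%, in line with the formula.

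**Allowing for leader counterbalancing.** Assume two leaders who swapped conditions between semesters; the plan does not give the scheme. An additive leader effect then cancels from the contrast. If a share λ of the class variance is leader variance, the variance ratio becomes 1 + [m(1 − λ) − 1] × ICC. At m = 22 and ICC 0.02:
- λ = 0: 1 + 21 × 0.02 = 1.42, type I error 10.0%.
- λ = 0.5: 1 + 10 × 0.02 = 1.20, about 7.4%.
- λ = 1: 1 − 0.02 = 0.98, about 4.8%.

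Simulations under this layout gave about 10%, 7.5% and 5%. The m = 22 column is therefore an upper scenario for each ICC.

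**Semester.** For a semester difference of d baseline-adjusted residual SDs, with half the participants in each semester, the planned SE is too large by √(1 + d²/4): 1.005, 1.031 and 1.077 for d = 0.2, 0.5 and 0.8. With no semester effect nothing is lost.

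**Both together.** A 40,000-run simulation used four classes of 22, ICC 0.02 with no leader component, and an equal raw semester gap of 0.8 SD at baseline and follow-up. Type I error was 9.1% as planned, 9.8% with semester added alone, and 5.0% with semester and the SE multiplied by √DEFF. The last figure uses the true ICC, so it shows only that the multiplier works when the ICC is known.

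**Tipping point.** Significance is lost at ICC = [(z/1.96)² − 1]/(m − 1). For an illustrative z = 2.5, this is 0.627/21 = 0.030 at m = 22 and 0.627/11.5 = 0.055 at m = 12.5.

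**The case against.** The best defence is that the design already limits the problem. Leaders were counterbalanced across conditions, and if they were properly crossed, leader variance drops out of the contrast. This stands, and it makes the tabulated figures upper values. It does not remove correlation from peers or group dynamics, and the plan does not show how the crossing was done.

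Second, the ICC may be zero. Exposure was three 50-minute sessions, the outcome is behaviour towards a partner outside the class, no participant reported an enrolled partner, and participants were told not to discuss the intervention with anyone else. "Four participants indicated they discussed their treatment condition with other students", which is few. This also stands as a reason to expect a small ICC. However, that question concerned talk with other students about treatment condition; it does not measure the effect of discussion within the sessions.

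Third, four classes cannot support a reliable ICC estimate or ordinary cluster-robust errors. That is correct, and is why a sensitivity table is requested rather than a different primary model.

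Fourth, omitting semester is conservative, and adding it alone slightly raises the error rate when the ICC is positive. That is also correct, and is why semester should not be added without the class table.

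A reader might infer that the Aim 4c test has a 17% false-positive rate, or that its result is invalid. The documents do not support this: 17% needs the largest ICC tabulated, all 88 followed up, and no leader variance cancelled. Nor do they support a claim that omitting semester biases the treatment contrast, because allocation was balanced within semester.

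**Conclusion.** The concern holds as a qualified one. It is certain from the text that Aim 4c makes no allowance for shared classes and omits semester. The size of the class effect is not known. Given four equal classes of 22, a two-sided 5% test and no leader component, type I error is at most about 7.5%, 10% and 17% at ICC 0.01, 0.02 and 0.05. With four classes of 12.5 it is 6.3%, 7.7% and 11.8%. At ICC 0.02 with classes of 22, it is about 7.5% if half the class variance is leader variance and about 5% if all is, assuming leaders swapped conditions. At ICC 0 there is no inflation. The semester omission costs a little precision at most.

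This is a should-fix point held with medium confidence. A significant Aim 4c result keeps its nominal level only if the non-leader within-class correlation is near zero, and the plan does not say so.

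**What to change.** 1. Add a semester indicator to each Aim 4c model and show the planned estimate beside it.
2. Report the number and sizes of classes among participants with follow-up, and how leaders were crossed with conditions. Beside each Aim 4c result, give the SE multiplied by √(1 + (m − 1) × ICC) at ICC 0.01, 0.02 and 0.05, and the ICC at which significance is lost. Use the actual m (sum of squared class sizes over sum of sizes, if unequal). Note that the ICC is the non-leader part if leaders were crossed, and that the normal cutoff is approximate with so few classes.
3. Do not present the semester-adjusted test without this table.
4. Label both additions post hoc. The Blinding section says that all analyses were fixed in advance, and the footnote on covariate choice already reports analysis results.
5. If a significant result does not survive the range, state that it depends on near-zero within-class correlation.

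The cost is one degree of freedom and one table, provided that class membership was recorded. The drawbacks are wider sensitivity intervals and an ICC that must be assumed rather than estimated.
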